5.3.2 Subject Enrollment

The subject must satisfy all eligibility criteria prior to enrollment. The subject is considered enrolled in the study at the time they sign the informed consent form (which includes consent to have photo and video recordings of the eye surgery made), with the study eye selected by the Investigator at the first study visit (Pre-operative). It is understood the number of subject eyes enrolled at the first study visit may be slightly more than the target number of 334 treated eyes.

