5.3.3 Subject Completion

The subject has completed the entire study when the LASIK refractive surgery has been completed and the Sponsor receives completed eCRF documentation for all required visits and a study exit eCRF. Subjects who require further follow-up for an AE will be followed until the AE has resolved or remitted, **regardless of whether they have completed all study visits**.

A Study Exit eCRF must be completed for all subjects who complete or are early discontinued from the clinical investigation.

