5.3.4 Subject Discontinuation

A subject MAY discontinue prior to the final study visit due to an AE occurring during the study which requires further medical intervention. A subject MUST be discontinued prior to the final study visit if they voluntarily withdraw for any reason, it is the Investigator's decision that it is not in the best medical interest of the subject to continue participation in the study, or in the event of death of the subject.

Prior to discontinuing a subject who voluntarily withdraws, every effort should be made to contact the subject, schedule a final study visit, and obtain as much follow-up data as possible. Regardless of the patient voluntary withdrawal, adverse events should continue to be followed by the investigator until they have resolved or remitted. Subject withdrawals will be documented clearly on the source document and applicable eCRF.

Discontinued subjects who withdraw consent should be followed outside of the study protocol according to the Investigator's normal post-operative standard of care.

A Study Exit eCRF must be completed for all subjects who discontinue from the clinical investigation. The reasons for subject withdrawal and discontinuation of any subject will be documented clearly on the applicable eCRF and recorded.

Subjects who discontinue the study prior to the surgical procedure will be considered screen failures and will not be recorded on the eCRF. Subjects who are discontinued during/after study LASIK surgery will not be replaced.

B+L Study # 884 Protocol Ver 8.0

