- Uncorrected Distance Visual Acuity (UDVA), photopic conditions
- Distance Best Spectacle-Corrected Visual Acuity (BSCVA), photopic conditions
- Slit lamp examination
- Contrast sensitivity sub-study, mesopic conditions
- Schirmer's test without anesthesia
- Pachymetry
- Manifest refraction under cycloplegia
- Intraocular pressure (Tonometry)
- Dilated fundus exam (vitreous, optic nerve, retina, macula, cup/disc)

7.1.2 Operative Visit 2 – Day 0

Subjects will return to the clinic and be reassessed to confirm eligibility (i.e., confirm that there have been no changes since the Pre-Operative Visit that would make the subject ineligible). If the subject is no longer eligible or is unable to attend Operative Visit 2 within specified visit interval due to the impact of the COVID-19 pandemic, the subject must be discontinued (refer to Section 5.3.4 and Section 7.4.1.2). If the subject is eligible, surgery will be performed using the surgical procedure described in Appendix C. If Operative Visit 2 was impacted by COVID-19, the subject may be rescreened for eligibility so long as the inclusion/exclusion requirements of Section 5.3.1.1 and Section 5.3.1.2 are met.

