8. ADVERSE SAFETY EVENTS

Each eye treated must be examined for the presence or absence of adverse safety events at all visits, whether scheduled or not. The collection of safety events begins at the time the subject signs the informed consent form. Refer to Table 2 for instructions on events that require expedited reporting to the Sponsor.

For the purposes of this study, adverse safety events are defined broadly to include a range of events encompassing four hierarchical categories of risk, Adverse Events (AE), Unanticipated Adverse Device Effects (UADE), Complications/Potential Adverse Events, and Symptoms, each having an associated level of required CRF/IRB/Sponsor/FDA reporting (See Table 2 Table 2. Safety Event Reporting, "Safety Event Reporting").

The first category, AEs, represents the key safety events that are surveilled during the study (**Section 8.1**). The second category (**Section 8.2**), UADEs, represent rare unanticipated safety events directly attributable to the device.

	Symptoms	Complications/ Possible AEs	Adverse Events	UADEs	
Required Action			Record in AE CRF within 48 hours	Record in AE CRF and on UADE form within 48 hours	
	Recorded in Subject Questionnaires	Recorded in Postoperative CRFs	Investigator	Investigator reports to IRB within 10 working days or per IRB policy, whichever is shorter	
		Repo per II			Reports to IRB per IRB policy

Table 2. Safety Event Reporting

Tertiary safety events include anticipated Complications/Possible Adverse Events known to occur following laser refractive surgery (Section 8.4), and subjective Symptoms reported by subjects (Section 8.5).

A representative list of safety events that are associated with each risk category are summarized in Sections 8.1–8.5 below:

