6.5 Statistical Methods

6.5.1 Disposition of Subjects

Eye accountability will be presented by postoperative visit separately for all treated eyes, eyes treated for spherical myopia, and eyes treated for astigmatic myopia. The numbers and percentages of subjects who were available for analysis, discontinued from the study, ongoing, lost to follow-up, or missed the visit will be displayed. Percent accountability, defined as eyes available for analysis divided by (enrolled minus discontinued minus active eyes) will also be presented by visit.

The reasons for premature study discontinuation will not be summarized but will be listed. In addition, subject data listings will be provided that include exclusions from study populations and any inclusion and exclusion criteria violations.

6.5.2 **Protocol Deviations**

Protocol deviations will not be summarized but will be presented in a data listing.

As required under §21 CFR 56.108(a)(3) & (4), an Investigator should notify the Sponsor and reviewing Institutional Review Board (IRB) of any deviation from the investigational plan intended to protect the life or physical well-being of a subject in an emergency. The date of and reason for protocol deviations will be documented in all cases. Significant or major protocol deviations affecting the safety, rights, and welfare of the subject or the integrity of the study must be reported by the Investigator to the IRB immediately. Reporting of all other protocol deviations must adhere to the requirements of the governing IRB.

Protocol assessments will continue until the end of the study, unless the protocol deviations put the subject at risk or the subject's condition requires that he/she should be discontinued from the study.

Protocol deviations related to Coronavirus Disease 2019 (COVID-19) pandemic impact on assessments described in the protocol will be presented in a separate data listing.

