6.5.8.2 Adverse Safety Events

Each eye treated must be examined for the presence or absence of adverse safety events at all visits, whether scheduled or not. The collection of safety events begins at the time the subject signs the ICF. For the purposes of this study, adverse safety events are defined broadly to include a range of events encompassing four hierarchical categories of risk: AEs, UADEs, complications/potential AEs, and symptoms. Adverse events represent the key safety events that are surveilled during the study. Unanticipated adverse device events represent rare, unanticipated safety events directly attributable to the device. Other safety events include anticipated complications/potential AEs known to occur following laser refractive surgery and subjective symptoms reported by the subjects.

All AEs, UADEs, and complications/potential AEs will be presented by the AE categories in the eCRF. The data listings by subject will present the categories of AE in the eCRF along with their coded AE term using MedDRA, Version 22.0.

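### Protocol 5.3.4 keeps consented subjects who leave before surgery off the eCRF, against the plan's own rules on exit forms, enrolment and adverse event collection from consent

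*Protocol*

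**What the plan says.** The rule at issue is in the last paragraph of Protocol 5.3.4: "Subjects who discontinue the study prior to the surgical procedure will be considered screen failures and will not be recorded on the eCRF." Other provisions cover the same people.

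- **Enrolment.** Protocol 5.3.2: "The subject is considered enrolled in the study at the time they sign the informed consent form." SAP 6.2 says the same.
- **Exit form.** Protocol 5.3.3: "A Study Exit eCRF must be completed for all subjects who complete or are early discontinued from the clinical investigation." Protocol 5.3.4, one paragraph before the rule at issue: "A Study Exit eCRF must be completed for all subjects who discontinue from the clinical investigation." The sentence after that asks for the reason for any subject's discontinuation on the eCRF.
- **Safety collection.** Protocol Section 8: "The collection of safety events begins at the time the subject signs the informed consent form." SAP 6.5.8.2: "The collection of safety events begins at the time the subject signs the ICF." Protocol Appendix A and SAP Table 2 schedule adverse events at Visit 1, which may fall up to 60 days before surgery. Protocol 8.1 wants its listed events on the AE CRF within 48 hours.
- **Day 0.** For a subject who is no longer eligible, or who cannot attend Visit 2 in its interval because of COVID-19, Protocol 7.1.2 says "the subject must be discontinued (refer to Section 5.3.4 and Section 7.4.1.2"). It also allows rescreening after a COVID-19 disruption.
- **Screen failure.** The end of Protocol 5.3.1 and SAP 6.2 use the term for failing eligibility before surgery is scheduled. Protocol 5.3.4 applies it to any exit before surgery.
- **Reporting.** SAP 6.5.1 gives percent accountability by postoperative visit, "defined as eyes available for analysis divided by (enrolled minus discontinued minus active eyes"). SAP 6.5.3.2 promises an accountability table for the COVID-19 population, which includes subjects discontinued because of the pandemic. SAP 6.5.6.1 bases listings on treated subjects by default, and SAP 6.5.8.3 tabulates adverse events in treated eyes from the operative visit on.

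**The concern.** A subject who signs consent, completes Visit 1 and then leaves before surgery is enrolled, is under safety collection and has discontinued. Three sets of rules then call for eCRF entries, and the last paragraph of 5.3.4 forbids them.

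Two things are at stake. The first is completeness of safety data. Both documents say collection starts at consent, yet an event in an untreated subject would not reach the study database. The second is visibility of the step from consent to treatment. This is an open-label, single-arm study tested against fixed proportions in treated eyes only. A reader of the report will want to know how many consented eyes were not treated, and why. Under the rule as written, the database cannot answer that, and no planned table asks.

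**Working it through.** **1. The plan's own figures, and whether they depend on this rule.**

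Treated eyes needed = 300 / (1 − 0.10) = 333.3, rounded up to 334, as the plan states. The 10% is loss after treatment, so exits before surgery do not enter.

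For power at n = 300, one-sided 2.5%, take z = [(p1 − p0) − 1.96 × √(p0(1 − p0)/n)] / √(p1(1 − p1)/n):

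| Endpoint | p0 | p1 | z |
|---|---|---|---|
| MRSE within 0.50 D | 0.80 | 0.945 | (0.145 − 0.0453) / 0.01316 = 7.58 |
| MRSE within 1.00 D | 0.90 | 0.99 | (0.09 − 0.0339) / 0.00574 = 9.76 |
| UDVA 20/40 or better | 0.88 | 0.99 | (0.11 − 0.0368) / 0.00574 = 12.75 |

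Each gives power above 0.9999999, which agrees with the stated figure of more than 99.99%. Protocol 9.5 and SAP 6.5.3.1 define the analysis on eyes enrolled and treated, so none of this changes.

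**2. Can a site follow all the rules?** Take a subject who consents, has an adverse event from the Protocol 8.1 list after Visit 1, and withdraws before Day 0.

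| Rule | eCRF entry |
|---|---|
| Protocol 5.3.3 and 5.3.4, exit form | Required |
| Protocol 5.3.4, reason for discontinuation | Required |
| Protocol Section 8 and 8.1, adverse event | Required |
| Protocol 5.3.4, last paragraph | None |

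The first three rules contain no exception for exits before surgery. The SAP does not settle the matter. It repeats enrolment at consent and safety collection from consent, then tabulates treated eyes.

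**3. What survives outside the eCRF.** Protocol 5.3.4 documents withdrawals in source and has the investigator follow adverse events after voluntary withdrawal. Protocol 10.2 puts all medical information from each visit in source, and 10.5 retains source documents and signed consent forms. Protocol 8.1 sends listed events to the IRB. The gap is therefore in the eCRF and whatever is built from it.

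**4. Effect on the accountability formula.** Let T be treated eyes, U consented eyes not treated, D treated eyes discontinued and A active eyes.

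- U counted as enrolled and as discontinued: (T + U) − (D + U) − A = T − D − A.
- U not recorded at all: T − D − A.

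The two agree. The result changes only if U is counted as enrolled but not as discontinued. Protocol 5.3.4 and 7.1.2 both describe these subjects as discontinued, so the documents do not support that mix. The remaining fault is that *enrolled* in the formula does not carry the meaning that SAP 6.2 gives it.

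**5. The COVID-19 route.** Protocol 7.4.1.1 records that sites were asked to cancel pending treatments. Protocol 7.4.1.2 says all clinics paused for 7 weeks or more, that is at least 49 days, against a pre-operative window of at most 60 days. A subject whose Visit 1 was more than 60 − 49 = 11 days before the pause would be outside the window when a 7-week pause ended. Protocol 7.1.2 sends such a subject to 5.3.4 and so to the no-eCRF rule, unless rescreened. SAP 6.5.3.2 does not limit its COVID-19 population to treated subjects, so its table would draw on records that the protocol says should not exist.

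**The case against.** The strongest reply is that 5.3.4 states a general exit-form rule and then a specific exception that reclassifies these people as screen failures. The screen-failure sentence in 5.3.1 does not say that it covers the only class. Both points are fair, and the two screen-failure definitions are better called unaligned than contradictory. The exception still does not reach Section 8, SAP 6.5.8.2 or the adverse events scheduled at Visit 1, and it leaves the COVID-19 table in SAP 6.5.3.2 short of its subjects.

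The safety yield may also be small. Most events listed in Protocol 8.1 are flap, haze, interface or postoperative vision outcomes, which an untreated eye is unlikely or unable to have. That limits the consequence but does not remove the conflict. Nor is there a study outcome on which to select before surgery, so selection is something the report could not show rather than something the documents suggest.

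A reader might go further in three ways that the documents do not support:

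- **These subjects leave no trace.** Source records, retained consent forms and IRB reports remain (step 3).
- **Accountability cannot be computed, or falls well below its nominal level.** The formula subtracts discontinued eyes and is reported for treated eyes (step 4).
- **A large number of eyes is involved.** No rate is given. Protocol 5.3.2 expects enrolled eyes to exceed 334 only slightly, and SAP 6.2 allows for slightly more or fewer.

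**Conclusion.** The contradiction is explicit and nothing in either document resolves it. Followed as written, the last paragraph of 5.3.4 removes from the eCRF and analysis database any adverse event between consent and surgery in an untreated subject, the number of consented eyes not treated, and the reasons. It also removes subjects discontinued before surgery because of COVID-19 from the table that SAP 6.5.3.2 promises.

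The size cannot be stated, because the documents give no rate of drop-out before surgery; no count or accountability percentage should be attached to this point. The primary tests, the 334 eyes and the power stand. This is a defect of safety completeness and subject flow that should be corrected. It does not threaten the effectiveness conclusion.

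**What to change.** **Protocol.** In 5.3.4, delete the clause that keeps these subjects off the eCRF. Record each consented subject who leaves before surgery on a minimal eCRF page or a sponsor-held screening log: consent date, eye or eyes, eligibility result, reason not treated, and any adverse event since consent. If the log is chosen, say in 5.3.3 and 5.3.4 that it takes the place of the Study Exit eCRF for these subjects, and in Section 8 that it carries their adverse events. Use one definition of screen failure in 5.3.1 and 5.3.4, and carry it into SAP 6.2.

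**SAP.** Add a flow table from consented to treated eyes with reasons, including COVID-19. List adverse events that occur before surgery, including those in untreated subjects. In the 6.5.1 formula, replace *enrolled* by *treated*.

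**Cost.** No added visits or subjects, and no change to the primary analysis. There is a small data-entry burden at up to 12 sites, partly retrospective because subjects had been screened before protocol version 8.0. A sponsor-held log avoids a change to the data capture system.

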5.3.5 Lost to Follow-up

Subjects who do not return for the final visit, as defined by the visit window, and cannot be contacted, may be considered lost to follow-up. Subjects who do not return for the final visit will have at least 2 documented attempts made to contact the subject by telephone or email. If all other attempts fail, a certified, return receipt requested letter will be sent to the last known address.

All follow-up attempts will be documented and documentation will be kept with the subject's source documents, and the applicable eCRFs will be completed. Documentation of the contact attempts and, if appropriate, a copy of the certified letter will be maintained in the subject's study file. It is expected that lost to follow-up subjects will comprise < 10% of all study eyes.

The exit date for subjects who are lost to follow-up will be the date of the last study visit (scheduled or unscheduled) attended by the subject.

5.4 Investigators

The clinical trial will be conducted at up to 12 investigational sites located in the US. The study will be conducted by Investigators who are determined by the Sponsor to be suitably qualified by training and experience to conduct this study. Such training and experience should comply with the international standard ISO 14155-2011 "Clinical Investigation of Medical Devices for Human Subjects - Good Clinical Practice" (ISO GCP) and FDA/CDRH Medical Device Regulations.

A TPV Engineer in conjunction with the Bausch & Lomb Training Team, will conduct Physician and staff training at each site on the operation and use of the TENEO 317 Laser. In addition, the Training team will be on site for the initial few surgeries to guide and support the PI and study staff on the use of the equipment. Training will be conducted as per TPV specifications, in line with the TENEO 317 model 2 user manual and a technical and medical In-Service checklist, and culminating with a Certificate of Training, with training recorded on the Site Training Log. The Physician and staff also will be trained through the Study Reference Manual which speaks to training on procedures, subject discontinuation, reporting of AEs and protocol deviations.

In addition, the Sponsor reserves the right to temporarily suspend or prematurely discontinue this study either at a single site or at all sites at any time and for any reason. If such action is taken, Sponsor will discuss this with the investigator (including the reasons for taking such action) at that time. Sponsor will promptly inform all other investigators and/or institutions conducting the study if the study is suspended or terminated for safety reasons and will also inform the regulatory authorities of the suspension or termination of the study and the reason(s) for the action. If required by applicable regulations, the investigator must inform the IRB/IEC promptly and provide the reason for the suspension

or termination. Each investigative site should enroll a minimum of 20 subject eyes and no more than 15% of total enrollment. Efforts will be made by the Sponsor and the administrating CRO to ensure approximately the same number of eyes will be enrolled at each clinical site.

5.5 Study Duration

Eligible subject eyes that are enrolled into the study will be seen for approximately 9 months after LASIK refractive surgery.

5.6 Protocol Amendments and Follow-up of the Protocol

The content and data of this protocol have been reviewed and accepted by the Sponsor. If an amendment is needed, this will be added by the Sponsor. All amendments will be recorded with the justification of changes to the protocol.

6. STUDY MATERIALS

6.1 Description of Test Medical Device

Like its parent device (Technolas 217z Excimer Laser System), the TENEO 317 Model 2 (ver. 1.28 US SW) Excimer Laser Workstation is an ophthalmologic system based on excimer laser technology used for refractive surgery that offers very precise preprogrammed ablation patterns to reshape the cornea of the human eye. The TENEO 317 Model 2 (ver. 1.27.2 SW EU) received CE Mark approval in Europe in 2017. The TENEO 317 Model 2 (ver. 1.28 US SW) excimer laser employs optical scanning technology operating at 193 nm ultraviolet wavelength to photo-ablate corneal tissue and imparts a proprietary aspheric ablation profile. The TENEO 317 Model 2 system employs a small laser spot (1 mm diameter), a randomized laser spot targeting pattern at 500 Hz, and a beam fluence of 200 mJ/cm². Three different auxiliary lasers are used in the TENEO 317 Model 2 in order to assist the surgeon in aiming the treatment beam correctly on the eye to be treated. Since the excimer laser emits in the invisible UV range at a wavelength of 193 nm, an aiming laser (aiming beam) consisting of a red diode laser is coupled coaxially with the treatment beam. Additionally, there is a fixation laser which is a red flashing laser diode that provides a fixation target for the subject eye during the surgery. A focusing laser which is generated by a green diode laser serves to align the treatment level. Other main features of TENEO 317 Model 2 (ver. 1.28 US SW) excimer laser are:

- Flying Spot technology provided by scanner systems for maximum flexibility in personalized treatment profiles.
- Short treatment times by 500 Hz technology with 1 mm laser spots.
- Precision for positioning of the laser pulse due to state of the art dynamic rotational eye tracking and z-axis tracking.

• Standard treatment with an asphericity algorithm taking into account the preoperative asphericity of the cornea and the surgically induced spherical aberration.

Other hardware modifications have been made to the TENEO 317 Model 2 Excimer Laser System as compared to the approved Technolas 217z Excimer Laser System and these modifications have been tested and verified in a series of non-clinical studies conducted to verify design output meets the design input requirements.

